<https://sites.google.com/a/umn.edu/redcap-help/>). Both Fitabase and REDCap meet privacy and security required when conducting research responsibly. Were someone to gain access to the physical activity data, they would not be able to identify the participants because these files use unique Fitbit identification numbers only, not study identification numbers or personally identifying information. If this unlikely event happens, we will report it using procedures outlined above. Steps would then be taken to identify how the breach occurred and what needs to be done to correct it.

An example of a serious adverse event includes the possibility of physical or psychological distress during the administration of the Short Physical Performance Battery (SPPB), an observational measure of functional strength and balance. To minimize this risk, research staff are trained and their continued competence to perform the SPPB, according to a standard protocol, is monitored monthly. The standardized protocol includes instructions to elicit participant's comfort and willingness to proceed with each movement. If the participant or the research assistant are not comfortable proceeding, the movement is not pursued. Participants are offered a verbal and written copy of their SPPB scores. The SPPB is established as a safe test to use across older populations. Participants in our studies have not had serious adverse events, expected adverse events or unexpected adverse events during the SPPB. If this unlikely event happens, we will report this using procedures outlined above. Steps would also be taken to identify how the event occurred and what needs to be done to correct it.

Another example of a serious adverse event would be the death of a participant from chronic heart failure. While viewed as unexpected and unrelated to the behavioral intervention, death

from heart failure would nonetheless be a reportable, serious event. No further steps would be taken except to review, grade and report the event using procedures outlined above.

An example of an unanticipated problem would be if a participant became immobile during their participation in the study. As immobility is an exclusion, we would withdraw the subject from the study. This event will be reviewed, graded, and reported using procedures outlined.

Assessment of External Factors

The PI will conduct a semiannual assessment of external factors through a review of literature related to new developments in the areas of fall prevention, fall-reducing physical activity, behavior change strategies, and other approaches that may have an impact on the safety of participants or on the ethics of the study.

Interim Analysis

This study aims to test the effects of behavior change strategies combined with an evidence-based physical activity protocol. As such, the PI and study coordinator will generate semi-annual qualitative interim analysis reports on data obtained during phone calls and end-of-study surveys to understand issues related to the uptake, usability, and adoption of this intervention among this population: community-dwelling older adults. We will evaluate the screening and enrollment procedures, barriers to participation and retention, functional impact, acceptability, technology problems encountered if any, and user feedback from the participants, interventionists and community centers. Information gained from this structured process will be used to both guide the refinement of the current protocol and to inform the design of a larger implementation trial. There are no planned stopping rules for this study.

CHAPTER 19 – PROVISIONS TO PROTECT THE PRIVACY INTERESTS OF PARTICIPANTS

19.1: PROTECTING PRIVACY

Several facets of our research plan contribute to the protection of participants' privacy interest. First, trained research staff will interact with study participants. Only staff responsible for scheduling intervention meetings or data collection meetings will have formal access, via REDCap, to personal information such as address and phone numbers

Study Staff Training

Curricula and enduring training materials will center on a) the interventionist role; b) data collection and management; and c) PA-monitor support. Interventionists will be trained to deliver all manualized intervention content and gain these core competencies (renewed on an annual basis): facilitating small group discussions; maintaining a positive social milieu; delivering interpersonal (5) and intrapersonal behavioral change strategies (5); and delivering Otago.

Research assistants will be trained to collect and manage data and gain these core competencies: conduct structured interviews with older adults in ways that are non-threatening, friendly, and respectful and that enable the accurate collection of data for questionnaires and physical measurements; the accurate documentation and storage of data using secure

iPads and REDCap. Additionally, RAs will also be trained to manage PA-monitors by gaining these core competencies: PA-monitor set-up; initial 1:1 orientation of participants to PA-monitor use; assist participants to troubleshoot PA-monitor; secure PA data collection and storage using the Fitabase research database.⁶⁷

Experts within our research team will evaluate training curricula prior to delivery. The courses will be delivered via a combination of online and in-person strategies. All study staff will have continual access to the training course, manuals of procedures, and to the PI for reference and consultation as needed, as well as a Physical Therapist who specializes in older adult physical function, the SPPB, and the Otago protocol.

Finally, all study staff are trained regarding the responsible conduct of research, REDCap use, and good clinical practice for social and behavioral research.

To ensure good practices are maintained throughout the study during intervention meetings and data collection meetings, all study staff will be directly and indirectly supervised. Supervision will include observing that privacy of each participant is protected. Monthly process reports include a summary of privacy protection.

Second, intervention meetings will occur in rooms reserved for small group meetings. Such rooms are private, in that conversations within these rooms can only be heard by small meeting participants (study volunteers and trained interventionists). Visitors or other community center personnel or members will not be involved with these meetings. Interventionists have skills and abilities to facilitate small group conversations so that privacy is protected.

Third, data collection meetings will take place between trained study staff, research assistants, and individual participants. These meetings will occur either in a private room within a community center or within the participant's home, whichever is preferred by the participant.

19.2: ACCESS TO PARTICIPANTS

This project does not require access to medical records, student records, or any other sources of private information. However, the project does entail collected self-reported health as well as names and addresses, which are needed to coordinate intervention delivery, fall calendar mailings and data collection meetings. Date of birth is needed to calculate age at the beginning of the study, which is a demographic baseline characteristic; the aggregate of which we will report as part of the study findings.

Not Applicable

CHAPTER 20 – CONSENT PROCESS

20.1: CONSENT PROCESS (When consent will be obtained):

Consent will occur between screening and enrollment. Within 10 days of being screened for eligibility, those potential volunteer participants who qualify for participation and remain interested, will receive a copy of the informed consent for the study via US mail

and meet in person with study staff who are trained in consent procedures. During the informed consent meeting, the trained will explain the project in detail to each potential participant. The study will be described, including its purpose; procedures, data collection, randomization, the intervention; use of the PA-monitor; potential risks and benefits; time required; and who to contact if there are concerns about the study. Eligible participants, their families, partners, or providers will be encouraged to ask questions or meet with the PI privately to further clarify questions, prior to providing consent. The participant may also take the consent form home again to look it over and ask questions of the trained research or PI at a time that is convenient to them. Interested persons will be under no time constraints to join or decline their participation.

Participants who provide verbal and written consent will be enrolled in the study. The consent form will also be signed by trained study staff or the PI, [name] and filed in REDCap.

In addition to obtaining consent prior to study enrollment, ongoing consent will be ensured. During data collection meetings, trained research staff will remind participants that answering all questions is voluntary: they may refuse to answer any question within the interview and may discontinue the interview at any time. Similarly, the trained interventionist will remind participants during small group meetings that participation in intervention meetings is voluntary: they may choose to not participate or leave any of the 8 intervention meetings.

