There will be rare situations when a participant is enrolled and randomized in the study, but is unable to begin or complete the 8-week intervention due to unforeseen changes in their life such as the death of a family member or the sudden need for medical treatments. In such situations, participants will be given the option to: (a) delay their participation in the 8-week intervention portion of the study, (b) withdraw from the 8-week intervention, but undergo one or more of the post-intervention data collection meetings, or (c) withdraw from all aspects of the study. Trained study staff will identify and track such situations in REDCap.

If participants choose option (a), they will **not** be re-randomized. Rather, researchers will invite them to an 8-week intervention course/ condition to which they were originally randomized, but that is scheduled to occur in a later time-frame.

Research staff will repeat screening to determine continued eligibility.

- If participants remain eligible, research staff will repeat baseline assessments within 8 weeks of the participant's delayed start of the 8-week intervention.
- If participants become ineligible---, reason(s) for ineligibility will be documented.

The analyst will compare and report the results of repeated baseline measures for subjects who choose option (a) and remain eligible for the study. If the differences between the repeated baseline measures are not significant, the first set of values will be used in inferential analyses. If the differences between the repeated baseline measures are significant, the second set of values (those most proximal to the intervention delivery) will be used in inferential analysis. A description of this will be included in all reports.

Research Outcome Data Collection. Trained research assistants will collect all data. They will be trained to accurately collect and manage data and to interview older adults in ways that are non-threatening, friendly, and respectful. Data will be derived from in-person interviews, observations, monthly fall calendars, and objectively measured PA parameters from accelerometers within participant's commercially available PA-monitors.

In-person interviews include scripted, structured interviews asking questions from these validated tools (all widely used) at the following time points:

- Baseline only: Demographic*
 - Biological
- Baseline; immediately post-intervention; 6 months' post-intervention; and 12 months post-intervention:

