We believe participation in this research will yield benefits for participants. Mastery of physical activities within the Otago PA protocol will provide participants with skills and knowledge to practice these exercises safely at home or in other environments of their choice. The behavioral change strategies in the intervention have the potential to motivate participants continued engagement in PA. Participants will also receive a PA-monitor for self-tracking and support to use it as well as interpret its data.

CHAPTER 17 – DATA MANAGEMENT

17.1: DATA ANALYSIS PLAN

Statistical analysis. Descriptive statistics (means, standard deviations, ranges for continuous variables and counts/ percentages for categorical variables) will be used to summarize biologic, demographic, outcome, and exploratory measures by treatment arm, actual and projected accrual, attendance and retention rates, quality control data (e.g., missing data), and fidelity data. Tables, graphs and charts will be used to visualize data when appropriate. Enrollment summaries will be reviewed at weekly research staff meetings throughout enrollment phases and every month during non-enrollment phases. Differences by randomly assigned condition will be assessed with one-way ANOVA tests for continuous and Fisher's exact test or chi-square tests for categorical variables as appropriate. Any identified confounders will be adjusted for in subsequent analyses. All analyses will be pre-planned and conducted while masked to condition.

We will include all cases in analyses, regardless of intervention attendance rates or attrition. Missing data will be analyzed. We anticipate, based on preliminary research that the rate of missing data will be low and similar across conditions, but that it may be associated with severe illness that leads to dropout or inability to capture follow- up PA data. Thus, similar to preliminary analyses, we will conduct a sensitivity analysis of complete cases and imputing worst case carried forward.

Primary Aim: Intervention component effects on PA will be assessed using 2x2 full factorial ANCOVA models with duration of total PA as the outcome (average minutes per

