week). The factors, or independent variables, are interpersonal and intrapersonal components; each with two levels indicating exposure (No vs Yes). Different models will be developed for PA measured objectively. PA will also be measured via self-report. Each model will include baseline PA values as a covariate. Main and interaction effects of the components on the duration of PA will be tested immediately, 6 months, and 12 months post- intervention. Further, we will apply multilevel longitudinal data analyses to examine the variation of component effects across time-points (baseline; immediately post-intervention; 6 months' post-intervention; and 12 months' post- intervention), including interactions between components (e.g. interpersonal x intrapersonal x time), which will allow us to see when an older adult might benefit from additional support to maintain PA.

Secondary Aim: The secondary outcome of Falls will first be described using the number of falls, fallers, fall rate, and time to first fall post-intervention.⁷⁴ Given the expected distribution of falls, we will use negative binomial regression models to estimate the between-group difference in fall rates 12 months' post-intervention. Quality of Life data will be assessed using 2x2 full factorial ANCOVA and longitudinal analyses described for Aim 1 with total mean QOL as the outcome variable.

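### The falls model leaves out past-year falls, an unspecified significance test picks the baseline for delayed starters, and further covariates are not fixed in advance (minor)

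*Combined protocol and SAP*

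**What the plan says.** **Falls.** Section 17.1, Secondary Aim: "we will use negative binomial regression models to estimate the between-group difference in fall rates 12 months" after the intervention. No covariate is named. Section 5.2 (Screening) includes fall risk factors among the screening questions, and section 9.1 lists a fall within the past year as one of them.

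**Delayed starters.** Section 5.2 introduces these cases with "There will be rare situations when a participant is enrolled and randomized in the study" but cannot begin or complete the course. Those who choose a later course keep their allocation, are re-screened and, if still eligible, repeat the baseline. If the two baselines do not differ significantly, the first is analysed; if they do, the second is. The comparison must be reported. The test, its alpha and whether the decision is made per person, per variable or for the group are not stated.

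**Other covariates.** Section 17.1 says "Differences by randomly assigned condition will be assessed with one-way ANOVA tests for continuous" variables, with Fisher's exact or chi-square tests for categorical ones. The next sentence is "Any identified confounders will be adjusted for in subsequent analyses", followed by "All analyses will be pre-planned and conducted while masked to condition". For PA, "Each model will include baseline PA values as a covariate". For quality of life (QOL), "Quality of Life data will be assessed using 2x2 full factorial ANCOVA and longitudinal analyses described for Aim 1", so a baseline QOL covariate is implied. No other section supplies a covariate list or defines a confounder.

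**The concern.** Past-year falls is a plausible predictor of later falls and is already asked at screening. Leaving it out gives up precision on a secondary outcome at no saving.

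The baseline rule makes the analysis dataset depend on a test result. With few delayed starters the test has little power, so the same true change keeps the first baseline when few people delay and brings in the second when many do. Two analysts could follow the text and build different datasets. The second value is measured after randomisation and can enter the primary model. Baseline is also a time-point in the longitudinal PA model.

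In a randomised trial, differences between conditions in baseline variables arise by chance. If such differences select covariates, the selection carries no information on prognosis, and the model stays open until data are seen even though the analyses are called pre-planned.

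**Working it through.** **Plan's own figure.** Section 17.2 claims 80% power for fall rate ratios of .40 to .70 but gives no fall rate or dispersion, so it cannot be reproduced. The falls inputs below are assumptions, apart from completers: 308 × .85 = 262, or 131 per factor level.

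**(a) Falls.** Assumed: marginal dispersion 1; half fell in the past year; their rate is 1.5, 2 or 3 times that of the others; mean 1 or 0.5 falls per person-year. The 0.5 comes from the one-in-three annual figure in section 2.1: at dispersion 1, P(no fall) = 1/(1 + mean) = 2/3 gives mean 0.5.

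- Unadjusted variance per person: v = 1/mean + 1, which is 2.00 at mean 1 and 3.00 at mean 0.5.
- Adjusted: hold the marginal variance fixed and solve for the residual dispersion k'. Then v = 1/average of [μ/(1 + k'μ)] over the two groups.
- Example, mean 1, ratio 2: μ = 2/3 and 4/3; 1 + (10/9)k' + 1/9 = 2 gives k' = .8; the terms are .435 and .645, average .540; v = 1.852.
- SE of the log rate ratio = √(2v/131). Power at .70 = Φ(.357/SE − 1.96). Equivalent extra completers = 262 × (v unadjusted/v adjusted − 1).

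| Mean | Past-fall ratio | v | Variance cut | SE cut | Power at .70 | Extra completers |
|---|---|---|---|---|---|---|
| 1 | none | 2.00 | – | – | 53.2% | – |
| 1 | 1.5 | 1.943 | 2.9% | 1.4% | 54.4% | 8 |
| 1 | 2 | 1.852 | 7.4% | 3.8% | 56.4% | 21 |
| 1 | 3 | 1.703 | 14.8% | 7.7% | 59.9% | 46 |
| 0.5 | none | 3.00 | – | – | 38.5% | – |
| 0.5 | 1.5 | 2.949 | 1.7% | 0.9% | 39.0% | 5 |
| 0.5 | 2 | 2.866 | 4.5% | 2.3% | 40.0% | 12 |
| 0.5 | 3 | 2.722 | 9.3% | 4.7% | 41.7% | 27 |

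Fitted models on simulated trials (500 runs, n = 264, mean 1) agree: SE .173 falls to .172, .168 and .162, and type I error is .054 against .056.

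**(b) Baseline test.** Assumed: a paired t-test on the delayed group, repeat correlation .8, true shift 0.2 SD. The SD of the difference is √(2 × .2) = .632, and the noncentrality is (.2/.632)√m. The second baseline is then used in 9% of trials with m = 5 delayed starters, 15% with 10 and 39% with 30.

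Effect on the PA estimate, by simulation (5,000 runs; 264 completers, baseline-outcome correlation .6, retest correlation .7, shift 0.5 SD): using the second baseline for 3, 5 or 10 people moves it by .006, .0075 or .0105 SD on average. The reference SE is √(.64 × 4/264) = .0985. The significance verdict changes in about 1% of null trials and 2.5-3.7% at a true effect of .20. With 10 delayed starters, the SE goes from .0986 to .0994 if the outcome tracks the first baseline, and from .0994 to .0985 if it tracks the second.

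**(c) Covariates chosen by imbalance.** Assumed: a mechanical .05 threshold; 4 × 66 completers; baseline-outcome correlation .6; 12 or 16 candidates with pairwise correlation .3, one having partial R² of 0 or .10; 3,000 runs per setting. A given covariate is selected in .042-.055 of trials whether prognostic or not. When something is selected, the estimate moves by .009-.022 SD on average. The SE is .0984-.0987 with baseline only and .0984-.0991 with selection. Type I error is .046-.053.

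**The case against.** **The numbers are small.** True for (b) and (c), and section 5.2 itself expects few delayed starters. This is why the point is minor.

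**The covariate mechanism is inferred.** Section 17.1 puts the between-condition tests next to the confounder sentence but does not say that a significant difference makes a confounder. If the term means a variable related to outcome, the figures in (c) do not apply. This stands; what remains is that no criterion is given.

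**Stronger readings.** A reader might infer that the rule inflates type I error. The simulation of a mechanical rule does not show that, and masked analysis limits choosing covariates to favour a condition. A reader might also infer that post-randomisation covariates are invited, because the opening summary is to "summarize biologic, demographic, outcome, and exploratory measures by treatment arm, actual and projected accrual, attendance and retention rates". The text does not support this: other sentences separate that list from the tests, confounder does not ordinarily cover variables affected by treatment, and the Exploratory Aim handles such measures separately as mediators.

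**The second baseline has a rationale.** It lies closest to the start of the course, and for someone who never began it is still pre-intervention. That is fair. Which baseline to fix is a judgement; the objection is to letting a test decide. Nor can one say that using the second value raises the SE, since the direction depends on which value the outcome tracks.

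**The unadjusted falls model is valid.** It is, and the open confounder clause could reach it. Every prognostic input in (a) is assumed. The one-in-three figure is for people aged 65 and over, whereas this trial enrols people of at least 70 with a fall risk factor, so 0.5 may be low. The gain therefore runs from trivial to modest. A reader might also take the 38-53% unadjusted power as refuting section 17.2; without a stated rate and dispersion it does not.

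**Conclusion.** The point holds as a minor matter of analysis choice, in three parts.

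- **Falls: a free improvement.** The planned comparison is valid but less precise than it could be. Adjustment would cut the variance of the log rate ratio by about 2-15%, conditional on the assumed fall rate, dispersion, share of past-year fallers and strength of past falls as a predictor.
- **Delayed starters: a cheap improvement.** This is the one data-dependent rule that the text states outright. Its expected effect on the PA estimate is about .006-.011 SD under the assumed inputs, with the effect on the SE in either direction. That figure covers the ANCOVA covariate, not the longitudinal model. The gain is reproducibility and keeping the primary model's covariate pre-randomisation.
- **Other covariates: close to missing detail.** If chance imbalance does the selecting, it adds no precision and leaves the model open. The consequence for PA is small.

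**What to change.** 1. Add past-year falls (yes/no) to the negative binomial model. Cost: one degree of freedom; the item is already asked at screening.
2. Replace the significance test in section 5.2 with one rule fixed before outcome data are seen. For example, use the pre-randomisation baseline in the primary model for everyone, with the repeated baseline as a sensitivity analysis. The downside is that the first value lies further from the start of the course.
3. Make between-condition comparisons of baseline variables descriptive and delete the confounder sentence. Before any outcome data are examined, fix the covariates of the primary PA, QOL and falls models: the baseline value of the outcome for PA (by the same measure) and QOL, past-year falls for falls, and any prognostic baseline variables named by then. Label other adjusted models as sensitivity analyses.
4. Bar post-randomisation covariates from the primary effect models only. The mediation models and the repeated-baseline sensitivity analysis are then unaffected.

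All four are wording changes and need no new data.
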